12. DATA HANDLING AND RECORD KEEPING

12.1 Electronic Data Capture (EDC) System

The full study dataset will be collected for participants who enter the randomized phase of the study. The primary data collection system for ISCHEMIA-CKD will use a web-based electronic data capture (EDC) system, a validated Electronic Record, Electronic Signatures (ERES) compliant platform (21 CFR Part 11). All these data collected at any point in the trial except the economic and quality of life information, are entered into this EDC system.

12.2 Data Management and Quality

Any out-of-range values and missing or inconsistent key variables will be flagged and addressed at the site in real time during the data entry process. When a query is generated on a particular variable, a flag will be set in a field in the database enabling the system to track the queries and produce reports of outstanding queries. Queries can also be generated from manual review of the data forms. These queries will be entered into the database and tracked in the same manner as the computer-generated queries. At regular intervals, all data will be transferred from the EDC database to SAS for statistical summarization, data description, and data analysis. Further cross-checking of the data will be performed in SAS, and discrepant observations flagged and appropriately resolved through a data query system. The Statistical and Data Coordinating Center (SDCC) will perform internal database quality-control checks, and data audits throughout the course of the trial.

12.3 Data Confidentiality and Security

Computerized data will be accessible only by password, and a centralized monitoring system will record and report all access to data. The DCRI computer network is protected by a firewall. Electronic CRFs (eCRFs) will be identified by study number only, to ensure participant anonymity. No participant identifiers will be used in the presentation of data. Study records that might identify participants will be kept confidential as required by law. Except when required by law, participants will not be identified by name, personal identification number (e.g. social security number, social insurance number), address, telephone number, or any other direct personal identifier in study records. This information will be retained by each individual center and will not be disclosed to the Coordinating Center except as needed for centralized clinical, quality of life and economic follow-up of the participants. Participants will be informed that the study physician and his/her study team will report the results of study-related tests to the Coordinating Center and to the NIH. Participants will be informed that their records may be reviewed in order to meet federal, state or regional/local regulations. Reviewers may include the CCC/SDCC monitors, IRBs/ECs, the NIH, other government regulators as dictated by local law, or their delegates.

Ischemia tests will be stripped of identifiers during the upload process, with the exception of date of study in DICOM headers, by a vendor which will be responsible for ischemia test transfer and storage for this trial.

12.4 Training

All investigational site and core lab staff authorized to enter ISCHEMIA-CKD study data will receive training on the EDC system. Training records will be retained by the EDC Helpdesk at the SDCC.

12.5 Records Retention

Study records will be maintained by the site investigators for a period of three (3) years following the expiration of the grant or length of time as required by local regulations, whichever is longer.

13. SAFETY MONITORING PLAN

13.1 Data and Safety Monitoring Board

A Data and Safety Monitoring Board (DSMB) will be appointed by the NHLBI to monitor participant safety and to review performance of the trial. The DSMB will include on its roster a nephrologist. A DSMB charter that outlines the operating guidelines for the committee and the procedures for the interim evaluations of study data will be developed by the NHLBI and agreed upon by the DSMB. Reports will be prepared regularly by the SDCC in accordance with the plan outlined in the charter and as requested by the DSMB chair, and will include interim analyses of primary and secondary endpoints; additional safety events; and other information as requested by the committee. After each meeting, the DSMB will make recommendations to the NHLBI and the trial leadership about the continuation of the study. After approval by the NHLBI director, a summary of the DSMB report and recommendations will be forwarded by the CCC to investigators for submission to their local, regional and national IRB/Ethics Committees, as applicable. DSMB reports will be the primary mechanism for reporting safety concerns to NIH and IRBs.

13.2 Risks and Benefits

All procedures and tests performed in this study are commonly performed in clinical practice and have well defined safety profiles. Furthermore, all procedures performed in this study, are commonly performed for the patient population enrolled in the study, i.e., those with advanced CKD, SIHD and at least moderate ischemia. The risk of cath and revascularization will be minimized by the selection of experienced operators who meet study certification criteria. These risks are justified by the potential benefit (long-term reduction in events resulting from revascularization, as discussed in the background section).

Risks:

Cath/PCI/CABG Risks: Each of these procedures is performed in clinical practice for patients who meet eligibility criteria for the CKD trial. The major risks of these procedures include death, myocardial infarction and stroke. Other risks of catheterization and PCI include severe contrast reaction such as anaphylaxis, emergency CABG, bleeding, need for blood transfusion, contrast-induced AKI, AKI requiring dialysis and vascular access site complications including pseudoaneurysm, AV fistula, retroperitoneal bleed or infection. Other risks of CABG include return to operating room for bleeding, need for blood transfusion, infection, prolonged intubation, mediastinitis, AKI, AKI requiring dialysis and atrial fibrillation. Risks of these procedures vary in likelihood based on the patient's risk profile and are generally higher in the CKD cohort than in participants without CKD.

Risk Lowering Measures:

The risk of cath and revascularization will be minimized by the selection of experienced operators who meet study certification criteria. Strategies to minimize the volume of contrast used and reduce the risk of contrast-induced AKI are outlined in the MOO. These risks are

justified by the potential benefit (long-term reduction in events resulting from revascularization, as discussed in the background section). Study procedures are designed to manage and minimize risks through careful selection of the patients who participate in the trial. Participants will be monitored closely through the trial at many time points to check on their health. In addition, an independent DSMB will monitor safety of the participants throughout the study (see [section 13.1](#))

Benefits:

The ISCHEMIA-CKD trial results should provide evidence based data to support management of participants with CKD and SIHD. It is hoped the knowledge gained will be of benefit to others with a similar medical condition in the future.

There may be benefit from participation in this study by receiving the medications and lifestyle counseling that are proven to improve outcomes in patients as well as involvement of an additional team following the participants' health status. Participants may receive some medications and stents free of cost, as available.

13.3 Safety Monitoring Objectives and Rationale

The main safety objectives in ISCHEMIA-CKD are to characterize the risk profiles of the two randomized management strategies and to monitor for unanticipated risks to study participants. All medications and procedures to be used/performed in this study are commonly used/performed for clinical indications as part of standard of care and have well-defined safety profiles. Because no investigational device, drug, diagnostic test or therapeutic intervention is being tested in this comparative effectiveness trial, reporting is primarily governed by the Common Rule (45 CFR Part 46, Subpart A), as well as ICH Guidelines, IRBs and local regulations.

13.4 Adverse Events Reporting by Investigators

Data for monitoring participants' safety will be captured within the EDC database as part of the required study data. There are no additional study-specific reporting requirements. Site investigators should follow usual clinical practices at their institutions for reporting serious, unexpected events related to standard of care medications and devices to regulatory agencies.

13.5 Events to be Monitored

Safety monitoring in ISCHEMIA-CKD will be concerned with estimating event rates for the following types of clinical events:

1. Complications of cardiovascular tests (e.g. cardiac catheterization) and therapeutic procedures (e.g. PCI, CABG)
2. Events occurring in the time period between consenting to participate in the trial and being randomized.
3. Study endpoints.

1. Complications of cardiovascular tests and therapeutic procedures

All drugs, diagnostic tests and therapeutic procedures to be used in this trial have been extensively evaluated previously, have established safety profiles with known risks and benefits and are routinely used in clinical practice. Events listed below occurring within 72 hours of the procedure will be considered as a complication of the procedure. Some safety events related to specific tests and procedures captured within EDC, in addition to death and MI, include:

Cardiac catheterization and PCI:

1. Severe contrast reaction such as anaphylaxis
2. Periprocedural stroke
3. Emergency CABG

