8.1 Creatinine and Pregnancy Test

At the screening visit a serum creatinine test must be drawn if one is not available within the previous 90 days. In addition, a pregnancy test is required if the participant is pre-menopausal.

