8.2 Standard Blood Tests

In this population with established coronary disease, as part of standard practice the following tests will typically be obtained by the participant's treating physician: complete blood count, electrolytes, creatinine, glucose, liver transaminases, lipid profile, and HbA1c. If HbA1c results are available for nondiabetics they will be recorded. If these test results are not available within specified time windows around the randomization visit (see MOO), then the following should be obtained: complete blood count, lipid profile, and HbA1c (for diabetics only). Liver transaminases should only be obtained if not available before starting statin therapy. An attempt will be made to coordinate participant follow-up visits so that they occur close in time to routine follow-up visits with their physicians when routine blood tests are performed. At 6 month follow-up visits, if lipid tests (and HbA1c at annual visits for diabetics) are not available within specified time windows they will be obtained by the study coordinator or participants will be referred to their treating physicians for the tests. Creatinine values obtained clinically for participants at the three month follow-up visit and annually will also be recorded.

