
^I Additional lab required at randomization includes complete blood count Request from participant's physician, since it is expected that routine blood work will have been done within the last 6 months

^J May be requested.

^K For participants undergoing PCI: troponin and CK-MB pre-procedure and at 8-16 ± 2 hours post-PCI or at hospital discharge, whichever comes earlier. For participants undergoing CABG: troponin and CK-MB pre-procedure and at 18 ± 6 hours post-CABG. All biomarker measurements should be recorded on eCRF. A biomarker measurement should be obtained before and after all PCI and CABG procedures, whenever possible.

^L Send to ECG core lab; ECG required for all cardiac admissions and revascularizations; year 1 ECG optional (filed on site) and closeout.

^M ECG done following procedure (60±30 mins post-PCI, 3 days post-CABG).

^N Selected Seattle Angina Questionnaire/Rose dyspnea scale/EQ-5D.

^O At every follow-up visit the research team, in collaboration with the treating physician(s), will evaluate effectiveness of medical therapy and optimize guideline recommendations and study algorithms.

^P Planned cath and revascularization only in the INV group. See MOO for time windows for performing cath and revascularization after randomization. Optimal revascularization treatment should be targeted within 30 days after randomization in the Invasive strategy group. In the Conservative group, revascularization is reserved for participants with refractory angina symptoms or acute ischemic events.

Screening visit

- Patients with advanced CKD and at least moderate ischemia (see protocol [appendix A](#)) will be assessed as potential study candidates
- General medical and cardiac history will be reviewed for eligibility according to the inclusion/exclusion criteria in [section 4.3](#)
- Willingness of both the prospective participant and their physician for participation throughout the study will be confirmed
- All screened prospective participants will be recorded in the paper screening log
- Prospective participants meeting clinical and site-based ischemia inclusion and exclusion criteria and interested in participating in the study will be consented for the study
- Consented participants will receive a study ID number via IVRS/IXRS. These participants are considered “enrolled” (not randomized).
- Creatinine testing if it has not been done within the last 90 days
- Pregnancy test if premenopausal

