4. AKI
5. AKI requiring dialysis
6. Vascular access site complications including pseudoaneurysm, AV fistula, retroperitoneal bleed

CABG:

1. Return to operating room for bleeding
2. Prolonged intubation
3. Mediastinitis
4. Atrial fibrillation
5. AKI requiring dialysis

In addition the incidence of finding significant LM stenosis ($\geq 50\%$) on cardiac catheterization will be monitored and reported to the DSMB.

2. Events occurring in the time period between consent and randomization

In general, eligibility for randomization will not be known at the time of enrollment but will need to be confirmed after performing additional screening procedures (e.g. pregnancy test). As a result, several days may elapse before the participant is randomized. Frequency of clinical events (e.g. death, MI) occurring during this time period, prior to randomization, will be monitored and reported to the DSMB.

3. Events that are trial endpoints

Selected trial endpoints (e.g. all-cause mortality) will be monitored at regular intervals during the course of the trial for the purpose of protecting participants' safety. Event rates in each treatment group will be confidentially reviewed by the DSMB. These analyses will inform the DSMB's recommendation to stop or continue the study or modify the protocol (see [section 11.2.6](#)).

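### AKI short of dialysis is a listed 72-hour complication of catheterization and PCI, but no creatinine is scheduled around any procedure, so its rate rests on local testing and site reporting

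*Combined protocol and SAP*

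**What the plan says.** Section 13.5 of the combined protocol and SAP aims to estimate rates of procedural complications and fixes the window: "Events listed below occurring within 72 hours of the procedure will be considered as a complication of the procedure". It introduces the lists with "Some safety events related to specific tests and procedures captured within EDC, in addition to death and MI, include". The catheterization and PCI list has AKI as item 4 and AKI requiring dialysis as item 5. The CABG list has only the latter. No definition of AKI is given in the protocol.

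Creatinine appears in the plan as follows:

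- Screening (section 8.1): "a serum creatinine test must be drawn if one is not available within the previous 90 days".
- Around randomization (section 8.2): creatinine is named among tests usually available from routine care. The tests to be obtained if results are missing are the blood count, lipids and, for diabetics, HbA1c.
- Follow-up (section 8.2): "Creatinine values obtained clinically for participants at the three month follow-up visit and annually will also be recorded". No draw is required.
- At the procedure (section 9, Table 2): the column holds a safety assessment, cardiac biomarkers, an ECG and endpoint assessment. Footnote K reads: "For participants undergoing PCI: troponin and CK-MB pre-procedure and at 8-16 ± 2 hours post-PCI or at hospital discharge, whichever comes earlier". For CABG it again names troponin and CK-MB.

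The safety-assessment footnote points to section 13.4, which routes safety data through the EDC and adds no study-specific reporting requirement.

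**The concern.** Short of dialysis, AKI is recognised mainly by a change in creatinine. That needs a reasonably recent value before the procedure and at least one value after it, inside the window. The plan schedules neither. Whether an episode is seen depends on what the treating hospital happens to measure and what the site then enters.

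The event matters in this trial. Section 2 names contrast-induced AKI first among the specific procedural risks for these participants. Section 4 presents limiting contrast exposure to half of them as a design advantage. Section 13.3 makes the risk profiles of the two strategies a main safety objective, and section 13.1 puts additional safety events in the DSMB reports and a nephrologist on the board. A rate that varies with local testing habits is hard for that board to interpret. If low testing goes unnoticed, the rate can understate the kidney risk of the invasive strategy.

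**Working it through.** No power, sample-size or alpha figure is involved, so there is no stated figure to reproduce. The check compares the timing of each planned creatinine with the 72-hour window.

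**Inputs**

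- Window: 72 hours = 3 days (13.5).
- Oldest acceptable creatinine at screening: 90 days (8.1).
- Consent to randomization: target 15 days (4.1).
- Randomization to catheterization: target 30 days (4.1).
- Three-month visit: taken as about day 91 after randomization (assumption).
- Post-PCI blood draw: 8-16 ± 2 hours, or discharge if earlier (Table 2, footnote K).

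**Age of the last planned creatinine at catheterization** = age at screening + days to randomization + days to catheterization, with consent taken to be at screening.

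- Drawn at screening: 0 + 15 + 30 = 45 days.
- Oldest accepted value: 90 + 15 + 30 = 135 days.

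Both are upper ends when the targets are met. Faster scheduling shortens them and missed targets lengthen them.

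**Gap from catheterization to the next planned creatinine** = 91 − day of catheterization.

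- Catheterization on day 30: 91 − 30 = 61 days.
- Catheterization on day 0: 91 − 0 = 91 days.

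Both far exceed 3 days, and the value is recorded only if care happened to produce it. No planned post-procedure creatinine falls in the window for a protocol-assigned procedure.

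**What the existing post-PCI draw would cover.** The latest scheduled time is 16 + 2 = 18 hours. That leaves at least 72 − 18 = 54 hours of the window after the draw, and more if discharge comes first. A catheterization without revascularization has no footnote K draw.

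**Illustration only.** Suppose testing is unrelated to AKI and an untested participant contributes no reported event. Then apparent rate = true rate × share with a creatinine in the window. The share is not in the documents; 30% to 90% is assumed. Section 2 cites incidences from <1% to >30%.

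| True rate | Apparent rate at 30% tested | At 90% tested |
|---|---|---|
| 1% | 0.3% | 0.9% |
| 10% | 3% | 9% |
| 30% | 9% | 27% |

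The spread shows how strongly the reported figure depends on an unknown testing share. It does not estimate the shortfall.

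**The case against.** The strongest reply is that this is a comparative-effectiveness trial of standard procedures which relies on routine-care results. Section 8.2 expects creatinine to be measured in ordinary practice, and section 13.5 describes complications captured as events in the EDC, not derived from study samples. The Manual of Operations, eCRF, DSMB charter and DSMB analysis plan are not in the documents and may hold a definition of AKI, a field for local values or a denominator rule. No endpoint or test is affected. Much of this stands. It reduces the charge to probable under-ascertainment and unstandardised measurement. It does not supply a creatinine, and where section 13.2 cites the Manual on contrast AKI, it does so only for measures to reduce the risk.

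Several stronger readings are tempting but not supported:

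- *The AKI rate cannot be obtained at all.* Sites can report AKI from local tests, and AKI requiring dialysis needs no scheduled creatinine.
- *The defect extends to CABG, or sections 13.2 and 13.5 conflict.* Section 13.2 does say "Other risks of CABG include return to operating room for bleeding, need for blood transfusion, infection, prolonged intubation, mediastinitis, AKI, AKI requiring dialysis", whereas the CABG list in 13.5 has only "5. AKI requiring dialysis". But 13.5 is openly a partial list, and transfusion, also named as a CABG risk in 13.2, is likewise absent from it.
- *Untested participants are counted as event-free, or dialysis participants stay in the denominator.* The documents state no rule either way.
- *A specific shortfall can be quoted.* The share tested and the share not on dialysis are not given. A rate among all participants must also not be set against a true rate among those not on dialysis.
- *The rate is certainly biased low.* If clinicians test those at higher risk, the shortfall is smaller. An old baseline in declining kidneys can also produce false positives.

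**Conclusion.** The point holds for AKI short of dialysis after catheterization and PCI. No creatinine is planned before or within 72 hours after any procedure. The last planned value may be up to 45 days old at catheterization, or up to 135 days old where a 90-day-old value was accepted, if the timing targets are met. The next planned value is roughly 61 to 91 days after a protocol-assigned catheterization, and is not guaranteed.

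The monitored rate is therefore exposed to local testing and reporting practice. Under-ascertainment is the likely direction, not a proven one, and its size cannot be computed from the documents. The conclusion assumes that the unseen Manual and eCRF do not already require timed creatinine values. The primary analysis is untouched. This is a worthwhile, inexpensive improvement to a safety measure the protocol itself chose to monitor.

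**What to change.** (a) In Table 2 and footnote K, for participants not on dialysis, add creatinine to the pre- and post-PCI draws already planned. On the eCRF, record every local creatinine within 72 hours, with its time, for all catheterizations. This must include those without revascularization, which have no footnote K draw.

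(b) In section 13.5, report AKI among participants not on dialysis at the procedure. Beside the rate, give the number with a pre-procedure value and at least one value in the window, the timing of the last value, and, separately, the number not assessed. Do not present a single early post-procedure value as complete assessment of the 72 hours. Whether a later draw is needed is for the sponsor to settle.

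The cost is one extra analyte on samples already taken, one eCRF field and some wording for the DSMB tables. The limitation is that the early post-PCI draw will miss later rises, so the rate must be read with the timing and not-assessed counts.

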Participants with advanced CKD are at increased risk for complications of the assigned invasive procedure, specifically contrast-induced acute kidney injury (AKI),^{15,16} dialysis, major bleeding and short-term risk of death. However, there is controversy in the medical literature regarding the incidence (<1% to >30%), effective treatment (saline hydration, N-acetyl cysteine, or sodium bicarbonate) and prognosis of contrast induced AKI (<0.5% to >5% requiring dialysis).¹⁷⁻²⁰ In addition although contrast induced AKI have been associated with increase in short-term mortality residual confounding in these studies makes interpretation difficult. Moreover it is unknown if these short-term increased risks are offset by long-term benefits. Limited observational study in the CKD cohort suggests a survival benefit of revascularization when compared with medical therapy alone long-term,²¹⁻²⁴ despite increase in short-term risks. However, the medical therapy in these trials was not optimized, drug eluting stents were rarely used and there is undoubtedly inherent selection and ascertainment bias with observational studies. The above has resulted in **substantial clinical equipoise in the management of these patients with the rates of revascularization of only around 10-45%.**^{21,23,25} The results of ISCHEMIA-CKD will have profound implications for guidelines, health policy, and clinical practice.

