10. ADJUDICATION OF CLINICAL EVENTS

An independent clinical event adjudication committee (CEC) will review and adjudicate all primary endpoint events and selected secondary endpoints in a blinded fashion based on study definitions. Endpoints to be adjudicated include death (including cause), myocardial infarction, resuscitated cardiac arrest, hospitalization for unstable angina, hospitalization for heart failure, and stroke. Because the trial is not blinded, to mitigate bias in the ascertainment of events, several strategies will be used to identify (“trigger”) all suspected endpoints in all participants including carefully constructed data collection tools that focus sites on key endpoint events, screening of ECG core lab data, site investigator and coordinator education about CEC procedures, and processing of events found by physicians during review of source documents pertaining to already identified endpoints. Care will be taken to blind reviewers to any information that could identify the participant or could reveal the randomized management strategy assignment. CEC members do not have access to management strategy assignment in order to avoid bias, which is an important process issue in this unblinded trial.

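### Kidney injury and dialysis are listed only as complications within 72 hours of a procedure, so the plan as written does not characterize kidney risk by randomized strategy

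*Combined protocol and SAP*

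**What the plan says.** Section 13.3 (Safety Monitoring Objectives and Rationale) gives as a main safety objective to "characterize the risk profiles of the two randomized management strategies". Section 2 (Background and Rationale) names contrast-induced AKI and dialysis among the specific added risks of the invasive procedure in this population, and says "it is unknown if these short-term increased risks are offset by long-term benefits".

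Section 13.5 (Events to be Monitored) names three kinds of event: procedure complications, events between consent and randomization, and study endpoints. Kidney events stand only in the first. The list opens with "Some safety events related to specific tests and procedures captured within EDC, in addition to death and MI, include", and its time rule is "Events listed below occurring within 72 hours of the procedure will be considered as a complication of the procedure". The catheterization/PCI list has both AKI and "AKI requiring dialysis"; the CABG list has only the latter, although Section 13.2 names AKI and AKI requiring dialysis as separate CABG risks.

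Review by arm is stated in Section 13.5 under trial endpoints: "Event rates in each treatment group will be confidentially reviewed by the DSMB". Those endpoints include no kidney event (Sections 3 and 11.2.2). The adjudicated set has none either: "Endpoints to be adjudicated include death (including cause), myocardial infarction, resuscitated cardiac arrest, hospitalization for unstable angina, hospitalization for heart failure, and stroke" (Section 10). Interim comparisons by strategy focus on all-cause death and the primary composite (Section 11.2.6). The only kidney measurement specified in both arms during follow-up is in Section 8.2: "Creatinine values obtained clinically for participants at the three month follow-up visit and annually will also be recorded".

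**The concern.** A risk profile of a randomized strategy needs events counted from randomization, in everyone randomized, whatever was done to them afterwards. A count triggered by a procedure does not provide this. The eligible set for the count is formed after randomization, and its size differs by design: catheterization is planned for all INV participants and reserved in CON for failure of medical therapy. A tabulation of these counts by arm would largely show who had a procedure.

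Two kinds of kidney event are lost. One is a dialysis start in a participant who never had a procedure, which is part of the background risk against which INV should be judged. The other is a dialysis start more than 72 hours after a procedure, in either arm.

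At stake is the trial's ability to report whether a strategy that exposes people with advanced CKD to contrast and surgery brings more of them to dialysis. Dialysis starts that are not captured prospectively may be hard to recover at closeout.

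**Working it through.** **1. Where a kidney event can be counted.**

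| Place in the plan | Kidney event? | Counted by randomized arm? |
|---|---|---|
| Primary and secondary endpoints (Sections 3, 11.2.2) | No | Yes, for the listed endpoints |
| Adjudicated events (Section 10) | No | Not applicable |
| Interim comparisons (Section 11.2.6) | No | Yes, for death and the primary composite |
| 13.5, procedure complications | AKI (cath/PCI only); AKI requiring dialysis (all) | Not stated; triggered by a procedure, 72 hours |
| 13.5, consent to randomization | Examples are death and MI | Before randomization |
| 13.5, trial endpoints | No | Yes |
| Creatinine (Section 8.2, Table 2 note H) | Values only, if obtained clinically | No threshold, outcome or analysis attached |

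No row combines a kidney event with counting by arm from randomization.

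**2. Check of the method on the plan's own figures.** The plan gives no figure for a kidney outcome, so the formulas are checked on the power and margin-of-error tables (Section 11.1.1). Inputs: 500 per group, 3.7 years, 1% loss per year, exponential times, CON four-year rate 60%, relative reduction 15%.

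- Hazards: −ln(0.40)/4 = 0.2291 (CON) and −ln(0.49)/4 = 0.1783 (INV); hazard ratio 0.779. Loss hazard: −ln(0.99) = 0.01005.
- Events per arm = 500 × λ/(λ + loss) × (1 − exp(−(λ + loss) × 3.7)), giving 281 + 238 = 519.
- Power = 81.4%, against 81% stated. Margin factor = exp(1.96 × 2/√519) = 1.188, against 1.19 stated.

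Reductions of 17% and 19% give 89.7% and 95.0%, against 90% and 95%. These tables are not in dispute.

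**3. What the 72-hour count could show.** Section 2 cites under 0.5% to over 5% requiring dialysis. Only participants not already on dialysis can newly need it, and their share is not given. Assume 300 to 600 in total, or 150 to 300 in INV, and read the range as a risk per participant: 150 × 0.005 = 0.75 to 300 × 0.05 = 15 events. If the range is instead a share of AKI cases, the count is smaller.

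**4. What an intention-to-treat dialysis outcome could show.** Assumptions: n = 300 to 600 in both arms together; death hazard h = −ln(0.5)/4 = 0.1733 per year (Section 2 projects four-year mortality above 50%); 3.7 years; no loss to follow-up; equal split. With dialysis hazard i:

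events = n × i/(i + h) × (1 − exp(−(i + h) × 3.7)); margin factor = exp(1.96 × 2/√events).

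Section 2 says people with advanced CKD are 5 to 10 times as likely to die as to reach end-stage renal disease. With constant hazards this gives i = h/10 = 0.0173 to h/5 = 0.0347. A rate of 8 to 15% per year is a more favourable assumption from outside the documents.

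| n | i per year | i/(i + h) | 1 − exp(−(i + h) × 3.7) | Events | Margin factor |
|---|---|---|---|---|---|
| 300 | 0.0173 (ratio 10) | 0.0909 | 0.506 | 14 | 2.87 |
| 600 | 0.0347 (ratio 5) | 0.1667 | 0.537 | 54 | 1.71 |
| 300 | 0.08 | 0.316 | 0.608 | 58 | 1.68 |
| 600 | 0.15 | 0.464 | 0.698 | 194 | 1.32 |

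For death or dialysis initiation, events = n × (1 − exp(−(i + h) × 3.7)). This gives 152 to 322 under the ratio (margin factor 1.37 to 1.24). Since i/(i + h) is then 9 to 17%, that composite would be mostly deaths.

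**The case against.** Several points on the other side stand.

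- The objective in Section 13.3 is to characterize, not to compare. A reader might infer that the protocol promises a formal between-arm kidney test and breaks the promise. It promises no such test.
- A reader might infer that only INV participants can contribute kidney events. The text does not support this. Section 13.5 is not limited to INV, the procedure part of Section 9 covers revascularization in both strategies, and Sections 6.1 and 6.6 allow catheterization in CON for stated reasons. No CON catheterization rate is given, so how uneven the counts would be is unknown.
- The 72-hour sentence attributes an event to a procedure; it does not forbid recording later events. The list is worded as partial. Section 13.1 puts a nephrologist on the DSMB and allows additional safety events and further requests. The DSMB analysis plan, the later SAP and the manual of operations could define a kidney outcome. It would therefore be too strong to say that nobody could ever see later dialysis starts.
- Creatinine and hospitalizations are collected in both arms.
- The intention-to-treat analyses of death and MI address part of the background's question about net benefit.

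These points narrow the concern without removing it. Open-ended wording does not commit anyone to a strategy-level kidney summary. Creatinine recorded only when clinically obtained, at three months and yearly, has no outcome attached and says nothing direct about dialysis. Death and MI do not show whether survivors reached dialysis.

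**Conclusion.** The point holds in a limited form. As written, the plan counts AKI and new dialysis only within 72 hours of a procedure, in whichever arm it occurs, and does not characterize kidney risk by randomized strategy. The omission of AKI from the CABG list, against Section 13.2, is a small inconsistency of its own.

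It is a gap in a safety objective. It does not touch the primary analysis or the sample size, and should be closed by amendment. If an outcome of this kind is already defined in a companion document, a cross-reference in Section 13.5 would settle it.

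A reader might infer that an added dialysis outcome would give a decisive answer. The documents point the other way: with the ratio in Section 2, the hazard ratio would be known only to within a factor of about 2.9 to 1.7. Even 8 to 15% per year gives 1.68 to 1.32. All these figures rest on the assumed number not on dialysis, 50% four-year mortality and constant hazards.

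**What to change.** Keep the 72-hour procedural list and add AKI to its CABG part, to agree with Section 13.2. Add to Section 13.5 and the SAP an intention-to-treat safety outcome, reported by arm to the DSMB and in the final report:

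- time from randomization to first dialysis among participants not on dialysis at baseline, with death as a competing event;
- the composite of death or dialysis initiation in the same participants;
- each with a 95% confidence interval, described as estimation and not as a powered test.

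State in Section 8.2 or the SAP what use, if any, will be made of the recorded creatinine values.

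The cost is a dialysis-start item on the follow-up eCRF, if not already collected, and one table. The documents list medical-status and hospitalization assessments at each follow-up visit but do not say that dialysis status is asked, so this must be checked first. No new visit or test is needed. The limitation is that the outcome would be site-reported and unadjudicated in an open trial, which should be stated beside the result.
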